4.4 Schedule of assessments

Table 1 Schedule of Assessments (Cohort 1)

		DSP-5423 (tablet) treatment phase (6 weeks)						DSP-5423P treatment phase (52 weeks)												Follow-up phase (1-2 weeks)	
Visit No.	-	1	2	3	4	5	6	101	102	103	104	105	106	107	108	109	110	111	112	113	
Study timeline ^{a)} Week	-	Timeline from initiation of DSP-5423 (tablet) administration						Timeline from initiation of DSP-5423P application												Follow-up visit Discontinuation 6~17 days after completion of treatment or discontinuation	
		Screening	Tab-Baseline	Tab-Week 1	Tab-Week 2	Tab-Week 4	Tab-Week 6 /baseline	Week 1	Week 2	Week 4	Week 6	Week 8	Week 12	Week 16	Week 20	Week 24	Week 28	Week 36	Week 44	Week 52	
		Tab -28-	Tab -2-1	Tab 5-11	Tab 12-18	Tab 26-32	Tab 40-43	5-11	12-18	26-32	40-46	54-60	78-92	106-120	134-148	162-176	190-204	239-267	295-323	351-379	At discontinuation +5
Visit window (Day)																					
Obtain informed consent	X																				
Patient demographics and medical history		X																			
Dispense study drug			X ^{d)}	X	X	X	X ^{e)}	X	X	X	X	X	X	X	X	X	X	X	X		
Study treatment compliance				X	X	X	X ^{e)}	X	X	X	X	X	X	X	X	X	X	X	X	X	
PANSS		X	X ^{d)}	X	X	X	X ^{e)}	X	X	X	X	X	X	X	X	X	X	X	X	X ^{g)}	
CGI-S		X	X ^{d)}	X	X	X	X ^{e)}	X	X	X	X	X	X	X	X	X	X	X	X	X ^{g)}	
DIEPSS			X ^{d)}	X	X	X	X ^{e)}	X	X	X	X	X	X	X	X	X	X	X	X	X ^{g)}	
C-SSRS			X ^{d)}	X	X	X	X ^{e)}	X	X	X	X	X	X	X	X	X	X	X	X	X ^{g)}	
DAI-10							X ^{e)}			X							X			X	
EQ-5D							X ^{e)}			X							X			X	
Skin irritation assessment							X ^{e)}	X	X	X	X	X	X	X	X	X	X	X	X	X	
Laboratory test ^{b)}		X	X ^{d)}		X		X ^{e)}		X		X		X		X		X	X	X	X ^{g)}	
Pregnancy test ^{c)}		X																		X	
12-lead ECG		X	X ^{d)}		X		X ^{e)}		X		X		X		X		X	X	X	X ^{g)}	
Body weight		X	X ^{d)}	X	X	X	X ^{e)}	X	X	X	X	X	X	X	X	X	X	X	X	X	
Body temperature, blood pressure, pulse rate		X	X ^{d)}	X	X	X	X ^{e)}	X	X	X	X	X	X	X	X	X	X	X	X	X	
Adverse event monitoring				◀																▶	

		DSP-5423 (tablet) treatment phase (6 weeks)						DSP-5423P treatment phase (52 weeks)												Follow-up phase (1-2 weeks)	
Visit No.	-	1	2	3	4	5	6	101	102	103	104	105	106	107	108	109	110	111	112	113	
Study timeline ^{a)} Week	-	Screening	Timeline from initiation of DSP-5423 (tablet) administration						Timeline from initiation of DSP-5423P application												Discontinuation
			Tab-Baseline	Tab-Week 1	Tab-Week 2	Tab-Week 4	Tab-Week 6 /baseline	Week 1	Week 2	Week 4	Week 6	Week 8	Week 12	Week 16	Week 20	Week 24	Week 28	Week 36	Week 44	Week 52	
		Visit window (Day)	Tab -28~	Tab -2~1	Tab 5~11	Tab 12~18	Tab 26~32	Tab 40~43	5~11	12~18	26~32	40~46	54~60	78~92	106~120	134~148	162~176	190~204	239~267	295~323	351~379
Blood sampling for PK					X			X ^{c)}				X					X		X	X	
Questionnaire																			X	X	

a) DSP-5423 (tablet) date of initial administration is the Tab-Day 1, and DSP-5423P patch initiation/beginning Date is the Day 1.

b) DSP-5423 (tablet) Visit 2 before administration initiation/beginning (perform), DSP-5423 (tablet) at the end of administration period (Visit 6) and at the end of DSP-5423P patch period (Visit 113) always in in fasting state/conditions (End fast 10 hours prior to blood collection/drawing/sampling). Perform to in fasting state/conditions as much as possible in the rest of the Visit.

c) Pregnancy only perform in premenopausal women available.

d) Perform prior to administration initiation/beginning of DSP-5423 (tablet). Prior therapy If antipsychotics are present, prior therapy after termination of antipsychotics, perform prior to DSP-5423 (tablet) administration initiation/beginning.

e) Perform prior to initiation/beginning of attachment of the DSP-5423P.

f) In the event of termination to DSP-5423 (tablet) administration period, treatment compliance status, DIEPSS, C-SSRS, laboratory test, bone pregnancy laboratory test, 12-lead electrocardiogram, body weight, bone termination, and Visit survey, observation, and laboratory test of the survey, observation, and laboratory test of the adverse event at the time of body temperature • blood pressure • pulse rate, among others, perform status, laboratory test, pregnancy, laboratory test, 12-lead electrocardiogram.

g) Investigational drug except perform prior to administration initiation/beginning of antipsychotics.

Table 2 Schedule of Assessments (Cohort 2)

			DSP-5423P treatment phase (52 weeks)														Discontinuation	Follow-up phase (1-2 weeks)
Visit No.	-	1	2	101	102	103	104	105	106	107	108	109	110	111	112	113		
Timeline from initiation of DSP-5423P application	-	Screening	Baseline	Week 1	Week 2	Week 4	Week 6	Week 8	Week 12	Week 16	Week 20	Week 24	Week 28	Week 36	Week 44	Week 52		
Visit window (Day)		-28~	-2~1	5~11	12~18	26~32	40~46	54~60	78~92	106~120	134~148	162~176	190~204	239~267	295~323	351~379	At discontinuation +5	6~17 days after completion of treatment or discontinuation
Obtaining informed consent	X																	
Patient demographics and medical history		X																
Dispense study drug			X ^{a)}	X	X	X	X	X	X	X	X	X	X	X	X			
Study treatment compliance				X	X	X	X	X	X	X	X	X	X	X	X	X		
PANSS		X	X ^{a)}	X	X	X	X	X	X	X	X	X	X	X	X	X ^{a)}	X ^{a)}	
CGI-S		X	X ^{a)}	X	X	X	X	X	X	X	X	X	X	X	X	X ^{a)}	X ^{a)}	
DIEPSS			X ^{a)}	X	X	X	X	X	X	X	X	X	X	X	X	X ^{a)}	X ^{a)}	
C-SSRS			X ^{a)}	X	X	X	X	X	X	X	X	X	X	X	X	X ^{a)}	X ^{a)}	
DAI-10			X ^{a)}				X						X			X	X	
EQ-5D			X ^{a)}				X						X			X	X	
Skin irritation assessment			X ^{a)}	X	X	X	X	X	X	X	X	X	X	X	X	X	X	
Laboratory test ^{b)}		X	X ^{a)}		X		X		X		X		X	X	X	X ^{a)}	X ^{a)}	
Pregnancy laboratory test ^{c)}		X														X	X	
12-lead ECG		X	X ^{a)}		X		X		X		X		X	X	X	X ^{a)}	X ^{a)}	
Body weight		X	X ^{a)}	X	X	X	X	X	X	X	X	X	X	X	X	X	X	
Body temperature, blood pressure, pulse rate		X	X ^{a)}	X	X	X	X	X	X	X	X	X	X	X	X	X	X	
Adverse event monitoring			←													→		
Blood sampling for PK							X						X			X	X	
Questionnaire																X	X	

a) The Day 1 is a DSP-5423P patch initiation/beginning Date.

b) Before the initiation/beginning of DSP-5423P attachment (Visit 2) and at the completion of the period of DSP-5423P attachment (Visit 113), perform should be performed at the in fasting state/conditions (End fast 10 hours before blood collection/drawing/sampling). Perform to in fasting state/conditions as much as possible in the rest of the Visit.

- c) Pregnancy only perform in premenopausal women available.
- d) Perform prior to initiation/beginning of attachment of the DSP-5423P. Prior therapy If antipsychotics are present, prior therapy after termination of antipsychotics, perform prior to initiation/beginning of DSP-5423P placement.
- e) Investigational drug except perform prior to administration initiation/beginning of antipsychotics.

5. Target sample size

Number of subjects enrolled: 200 subjects

- Number of subjects treated with DSP-5423P for 6 weeks and more in cohort 1: 50 subjects
- Number of subjects treated with DSP-5423P for 52 weeks in either cohort 1 or cohort 2: 100 subjects

The new enrollment can be terminated at the time when 100 subjects with 52-week exposure of DSP-5423P are collected, together with a separate confirmatory study [Confirmatory Study of DSP-5423P in Patients with Schizophrenia <Phase 3> (protocol: D4904020)].

6. Analysis population

Prior to database hard lock, a data review meeting will be conducted and subject assignments to analysis set/population will be determined.

6.1 Safety analysis population

Subjects with at least one application of DSP-5423P.

Efficacy analysis will also be performed based on the safety analysis population.

6.2 Pharmacokinetic analysis population

Subjects with at least one application of DSP-5423P, and with measurements of plasma bronanserin concentration after application of DSP-5423P.

7. Endpoints

7.1 Efficacy endpoints

- 1) Change in PANSS total score from baseline ^{note 1)}
- 2) Change in PANSS subscale total scores from baseline ^{note 1)}
- 3) Change in by PANSS 5 Factor Model total score from baseline ^{note 1)}
- 4) Change in CGI-S scores from baseline ^{note 1)}
- 5) Time to treatment discontinuation from the initial application of DSP-5423P

Note 1) Baseline of DSP-5423P treatment period

7.1.1 PANSS

The PANSS is an interview-based measure of the severity of psychopathology in adults with psychotic disorders. A person, who will be a certified rater for PANSS assessments, will receive specific training and education for the PANSS assessment provided by the Sponsor and will be certified by the Sponsor before his/her initial assessment of PANSS. The certified rater will rate 30 items on a 7-point scale of 1 to 7 and record dates and results of the assessments in the CRFs.

When the study treatment is completed or prematurely discontinued, PANSS will be rated before starting post-treatment with other antipsychotics.

The PANSS total score is the sum of all 30 item scores.

PANSS subscale

Positive subscale: Delusions, conceptual disorganization, hallucinatory behavior, excitement, grandiosity, suspiciousness/persecution, and hostility

Negative subscale: Blunted affect, emotional withdrawal, poor rapport, passive/apathetic social withdrawal, difficulty in abstract thinking, lack of spontaneity and flow of conversation, and stereotyped thinking

General psychopathology subscale:

Somatic concern, anxiety, guilt feelings, tension, mannerisms and posturing, depression, motor retardation, uncooperativeness, unusual thought content, disorientation, poor attention, lack of judgment and insight, disturbance of volition, poor impulse control, preoccupation, and active social avoidance

Each PANSS subscale score is the sum of item scores defined respectively as each subscale.

PANSS 5 factors models

Negative symptoms: Blunted affect, emotional withdrawal, poor rapport, passive/apathetic social withdrawal, lack of spontaneity and flow of conversation, and active social avoidance

Excitement: Excitement, hostility, tension, and poor impulse control

Cognitive disorders: Conceptual disorganization, difficulty in abstract thinking, mannerisms and posturing, disorientation, and poor attention

Positive symptoms: Delusions, grandiosity, suspiciousness/persecution, and unusual thought content

Anxiety/depression: Hypochondria, anxiety, feelings of guilt, depression, and preoccupation

PANSS 5 factor model score is the sum of item scores defined respectively as each factor.

7.1.2 Clinical Global Impression – Severity of Illness (CGI-S)

CGI-S is a research rating tool of the subject's current disease state on a 7-point scale of 1 to 7. The Investigators will receive specific training before their initial assessment of CGI-S. Dates of the assessments and the results will be recorded in the CRFs.

When the study treatment is completed or prematurely discontinued, CGI-S will be rated before the first post-treatment with other antipsychotics.

7.1.3 DSP-5423P patch duration

The treatment duration of DSP-5423P will be the one from the initial application date to the last application date of DSP-5423P. Termination of application (for any reason) will be an event and

completion of treatment will be a censor. That is to say, time to event based on treatment duration from start to termination of treatment will be analyzed. In this analysis, subjects who complete study treatment will be censored not as an event, considering those subjects can pursue study treatment even after treatment completion.

7.2 Safety endpoints

- 1) Adverse events (AEs) and adverse drug reaction (ADRs)
- 2) Extrapyramidal AEs and ADRs
- 3) Skin-related AEs and ADRs at the application site
- 4) Assessment of skin irritation reaction at the application site
- 5) Change in Drug-Induced Extrapyramidal Symptoms Scale (DIEPSS) Total Score (excluding overall severity) from baseline
- 6) Change in individual DIEPSS scores from baseline
- 7) Serum prolactin concentration
- 8) Electrocardiogram (ECG) parameters (QTc)
- 9) Concomitant use of antiparkinson drug
- 10) Assessment of suicides using Columbia-Suicide Severity Rating Scale(C-SSRS)
- 11) Laboratory test values, vital signs and body weight

7.2.1 Adverse event

In this study, relevant events occurred from the treatment initiation of DSP-5423 (tablet) to follow-up visit in cohort 1 and ones occurred from the initiation of DSP-5423P application to follow-up visit in cohort 2 will be captured as adverse events. An AE can, therefore, be any unfavorable and unintended sign (including an abnormal laboratory finding), symptom, or disease occurring after the administration of a medicinal (investigational) product, whether or not considered related to the medicinal (investigational) product.

In the cohort 1, AEs that occur during the DSP-5423 (tablet) treatment period and worsen during the DSP-5423P application period will be recorded as both AEs in the DSP-5423 (tablet) administration period and also as AEs in the DSP-5423P application period with start date as the onset date of the worsening AE. AEs that occur during the DSP-5423 (tablet) treatment period without further worsening in the DSP-5423P application period will be recorded as AEs only in the DSP-5423 (tablet) treatment period

7.2.2 Concomitant drug and concomitant therapy

The following information on all medications used from initiation of DSP-5423(tablet) treatment until the follow-up visit in cohort1 or initiation of DSP-5423P application until the follow-up visit

in cohort 2 will be recorded in the CRFs. For antipsychotics and antiparkinson drugs, the information on the usage for 7 days before screening and during wash-out period will also be recorded in the CRFs.

- Drug name, Route, Start date, Stop date, The reason for concomitant use, Drug category
- Daily dose (for antipsychotics and antiparkinson drugs only)

7.2.3 Laboratory test

Blood and urine samples will be collected for clinical laboratory tests. The Investigators will record the date of collection and whether or not the subject is under fasting conditions (at least 10 hours after the last meal) in the CRFs. All clinical laboratory tests will be performed centrally.

The clinical laboratory tests required by the protocol are listed in Table 3. Detailed instructions regarding clinical laboratory procedures, sampling, shipping, and reporting can refer to the instructions manual provided by the Sponsor.

Table 3 Contents of laboratory variables

Hematology test	white blood cell count, red blood cell count, hemoglobin, hematocrit, platelet count, differential white blood cell count (neutrophils, eosinophils, basophils, monocytes, and lymphocytes)
Biochemical laboratory test	total protein, total bilirubin, AST, ALT, ALP, γ -GTP, LDH, total cholesterol, triglycerides, BUN, creatinine, CK, Na, K, Cl, blood glucose, HbA1c, serum prolactin
Urinalysis (qualitative)	glucose, protein, occult blood, urobilinogen
Pregnancy test (premenopausal women of childbearing potential only)	Urine chorionic gonadotropin

7.2.4 Vital Sign and Body Weight

Investigator measure the following variable and record Dates of measurements and the results in the CRFs

- Systolic and diastolic blood pressures (sitting), pulse rate, body temperature (axilla), and body weight

7.2.5 12-lead ECGs

The Investigator will perform 12-lead ECG at rest and record the dates and times of assessments in the CRFs. The Investigator will retain ECG tracings and send them electronically to the central ECG reader. The central ECG reader will analyze ECG tracings and calculate the following ECG parameters: RR interval, QT interval, PR interval, QRS interval, and QTc interval (QTc Fridericia [QTcF] and QTc Bazett [QTcB]). The central ECG reader will report analysis results and ECG

parameters to the Sponsor and the Investigator. Detailed instructions regarding 12-lead ECG can refer to the instructions manual provided by the Sponsor

The principal ECG analyst will comprehensively evaluate the effect of study treatment on QTc prolongation.

- Bazett: $QT_{cB} \text{ (msec)} = QT \text{ (msec)} / (RR \text{ (sec)} \times 1000)^{1/2}$
- Fridericia: $QT_{cF} \text{ (msec)} = QT \text{ (msec)} / (RR \text{ (sec)} \times 1000)^{1/3}$

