11.3.6 Vital Signs and Body Weight

- Systolic and diastolic blood pressures (sitting), pulse rate, body temperature (axilla), and body weight will be measured. Dates of measurements and the results will be recorded in the CRFs.

11.3.7 12-lead ECGs

The Investigator will perform 12-lead ECG at rest and record the dates and times of assessments in the CRFs. The Investigator will retain ECG tracings and send them electronically to the central ECG reader. The central ECG reader will analyze ECG tracings and calculate the following ECG parameters: RR interval, QT interval, PR interval, QRS interval, and QTc interval (QTc Fridericia [QTcF] and QTc Bazett [QTcB]). The central ECG reader will report analysis results and ECG parameters to the Sponsor and the Investigator. Detailed instructions regarding 12-lead ECG can refer to the instructions manual provided by the Sponsor

The principal ECG analyst will comprehensively evaluate the effect of study treatment on QTc prolongation.

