8.5 Analysis Visit

Data of DSP-5423P treatment period is defined as the data captured on Day 1 through 7 days after the final application of DSP-5423P.

All data will be organized and analyzed according to the scheduled timing as outlined in Tables 1 and 2 Schedule of Assessments and according to the visit denoted in the CRFs. Unscheduled visits may not be used for any analysis unless otherwise specified. However, the data collected at the discontinuation visit within 7 days from the final application of study drug are mapped to the next scheduled visit of the actual discontinuation date. In listing, all data including unscheduled visit data should be presented.

1) CRF discontinuation visits in DSP-5423 (tablet) treatment period

Assessments and tests	Relative Day	Analysis Visit
PANSS, CGI-S, DIEPSS, body weight, body temperature, blood pressure, pulse rate	Tab-Day 1 to 11	Tab-W1, 2, 4, 6
	Tab-Day 12 to 18	Tab-W2, 4, 6
	Tab-Day 19 to 32	Tab-W4, 6
	Tab-Day 33 or later	Tab-W6
Laboratory test, ECG	Tab-Day 1 to 18	Tab-W2, 6
	Tab-Day 18 or later	Tab-W 6

The Tab-Day 1 is defined as the date of initial administration of DSP-5423 (tablet). CRF discontinuation visits in DSP-5423 (tablet) treatment period is defined as data on first non-missing (ex. no visit or results are missing) visit which meets all above requirements. Laboratory test and vital sign (body temperature, blood pressure, pulse rate) are performed visit handling for each item. Others are not considered as missing if they have any one component.

2) CRF discontinuation visits in DSP-5423P application period

Assessments and tests	Relative Day	Analysis Visit
PANSS, CGI-S, DIEPSS, C-SSRS,	Day 1 to 11	W1, 2, 4, 6, 8, 12, 16, 20, 24, 28, 36, 44, 52
	Day 12 to 18	W2, 4, 6, 8, 12, 16, 20, 24, 28, 36, 44, 52

Assessments and tests	Relative Day	Analysis Visit
Skin irritation assessment, body weight, body temperature, blood pressure, pulse rate	Day 19 to 32	W4, 6, 8, 12, 16, 20, 24, 28, 36, 44, 52
	Day 33 to 46	W6, 8, 12, 16, 20, 24, 28, 36, 44, 52
	Day 47 to 60	W8, 12, 16, 20, 24, 28, 36, 44, 52
	Day 61 to 92	W12, 16, 20, 24, 28, 36, 44, 52
	Day 93 to 120	W16, 20, 24, 28, 36, 44, 52
	Day 121 to 148	W20, 24, 28, 36, 44, 52
	Day 149 to 176	W24, 28, 36, 44, 52
	Day 177 to 204	W28, 36, 44, 52
	Day 205 to 267	W36, 44, 52
	Day 268 to 323	W44, 52
	Day 324 or later	W52
Laboratory test, ECG	Day 1 to 18	W2, 6, 12, 20, 28, 36, 44, 52
	Day 19 to 46	W6, 12, 20, 28, 36, 44, 52
	Day 47 to 92	W12, 20, 28, 36, 44, 52

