9.12.2 Laboratory test

Observed values and changes from baseline at DSP-5423P application period for the hematology, and blood chemistry parameters will be summarized by visits including LOCF endpoints. For urinalysis parameters, the number and percentage of subjects in each category of parameters will be summarized at baseline of DSP-5423P application period, each visit, and LOCF endpoint. All laboratory parameters and any abnormal laboratory values, which are all values beyond its own normal range at least one time whenever in DSP-5423P application period, will be listed respectively.

Criteria for Markedly Abnormal Post-Baseline Laboratory Values(MAPLV) for abnormal values in the hematology, and blood chemistry parameter can be found in Table 6. The frequencies and percentages of subjects who met MAPLV at least once in the post-baseline of DSP-5423P (including unscheduled visits), will be presented.

Table 6 Criteria for Markedly Abnormal Post-Baseline Laboratory Values

Hematology Parameter	Markedly Abnormal Range
Hemoglobin	Male: ≤ 11.5 g/dL
	Female: ≤ 9.5 g/dL
Hematocrit	Male: $\leq 37\%$
	Female: $\leq 32\%$
WBC	$\leq 2.8 \times 10^3/\mu\text{L}$
	$\geq 16 \times 10^3/\mu\text{L}$
Platelets	$\leq 75 \times 10^3/\mu\text{L}$
	$\geq 700 \times 10^3/\mu\text{L}$
Chemistry Parameter	Markedly Abnormal Range
ALT	$\geq 3 \times \text{ULN}$
AST	$\geq 3 \times \text{ULN}$
Alkaline Phosphatase	$\geq 1.5 \times \text{ULN}$
Na/Sodium	$\leq 130 \text{ mEq/L}$

	> 150 mEq/L
K/Potassium	< 3 mEq/L
	> 5.5 mEq/L
Cl/Chloride	< 90 mEq/L
	> 115 mEq/L
Blood Glucose (fasting)	< 50 mg/dL
	> 250 mg/dL
HbA1c	>= 7.5%
Total Bilirubin	> 2 x ULN
Blood Urea Nitrogen	> 30 mg/dL
Creatinine	> 2.0 mg/dL
CK	> 3 x ULN
Serum Prolactin	>= 5 x ULN
Triglycerides (fasting)	> 300 mg/dL
Total Cholesterol (fasting)	> 300 mg/dL

Note: A value is considered MAPLV if it is outside the Markedly Abnormal Range.

Note: Blood glucose, triglycerides, and total cholesterol are limited for blood samples collected in fasting state.

Box plot of observed value of the hematology and blood chemistry parameters will be provided by visits including baseline of DSP-5423P application period and LOCF endpoint.

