9.12.3 Vital sign and body weight

BMI is calculated based on the height at Screening and weight at each visit.

Observed values and changes from baseline at DSP-5423P application period for the vital sign, weight and BMI will be summarized by visits including LOCF endpoints. The vital sign, weight and BMI will be listed.

Criteria for Markedly Abnormal Post-Baseline Vital Signs (MAPVS) for abnormal values in the vital sign can be found in Table 7. The frequencies and percentages of subjects who met MAPVS criteria at least once in the DSP-5423P post-baseline (including unscheduled visits) will be

presented. Weights for subjects with values met MAPVS criteria in DSP-5423P post-baseline period (including unscheduled visits) will be listed.

Table 7 Criteria for Markedly Abnormal Post-Baseline Vital Signs

Parameter	Unit	Markedly low	Markedly high
Weight	Kg	>= 7% decreased from baseline	>= 7% increased from baseline

Box plot of observed value of the vital sign, weight and BMI will be provided by visits including baseline at DSP-5423P application period and LOCF endpoint.

For DSP-5423(tablet) treatment period in Cohort 1, observed values and changes from baseline in DSP-5423(tablet) treatment period for the vital sign, weight and BMI will be summarized by visits including LOCF endpoints. Box plot of observed value of the vital sign, weight and BMI will be provided by visits including baseline of DSP-5423(tablet) treatment period for both DSP-5423(tablet) treatment period and DSP-5423P application period in Cohort 1.

9.12.4 12-lead ECGs

Observed values and changes from baseline in DSP-5423P treatment period for ECG parameters (RR interval, QT interval, PR interval, QRS interval, and QTc interval (QTc Fridericia [QTcF] and QTc Bazett [QTcB])) will be summarized by visits including LOCF endpoints. Interpretation, which is ‘Normal’, ‘Abnormal’, or ‘Not evaluable’, will be summarized based on the number and percentage of subjects by visits including LOCF endpoints. In case that finding are identified in a subject, and his/her interpretation is ‘Normal’, the subject will be summarized as ‘Normal’. The ECG parameters will be listed. The ECG parameters for subjects who experienced ‘Abnormal’ at least once in the DSP-5423P post-baseline (including unscheduled visits) will be listed.

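### Two SAP definitions are wrong as written: the QTc formulas use RR in msec (results 31.6-fold and 10-fold too small), and the Table 6 note reverses the rule for markedly abnormal laboratory values

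*SAP*

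**What the plan says.** **QTc.** SAP 7.2.5 gives Bazett's QTc in msec as "QT \text{ (msec)} / (RR \text{ (sec)} \times 1000)^{1/2}", and Fridericia's with the same denominator raised to 1/3. The same section assigns the calculation to the central reader: "The central ECG reader will analyze ECG tracings and calculate the following ECG parameters". Protocol 11.3.7 does likewise ("calculate the following ECG parameters: RR interval, QT interval, PR interval, QRS interval, and QTc interval") and prints no formula. SAP 9.12.4 summarises the same list by visit ("for ECG parameters (RR interval, QT interval, PR interval, QRS interval, and QTc interval"). Its Table 8 counts subjects with QTc above 450, 480 and 500 msec and with increases above 30 and 60 msec.

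**Laboratory values.** SAP 9.12.2, Table 6, has a column headed Markedly Abnormal Range. It holds abnormal values, for example ALT at or above 3 x ULN and potassium below 3 or above 5.5 mEq/L. The text above the table counts subjects as follows: "The frequencies and percentages of subjects who met MAPLV at least once in the post-baseline of DSP-5423P". The note under the table reads: "A value is considered MAPLV if it is outside the Markedly Abnormal Range".

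**The concern.** A heart-rate correction must leave QT unchanged when RR is 1 sec. The printed formulas do not, and their results are on a different scale from the cut-offs in Table 8. Programmed as printed, they would leave the QTc prolongation table essentially empty.

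The Table 6 note turns the rule for a single value around: a normal ALT would qualify as markedly abnormal, and an ALT of 5 x ULN would not.

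Safety is the primary objective, and QTc and laboratory values are named safety endpoints (SAP 4.1 and 7.2), so their definitions should be correct as they stand.

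**Working it through.** **Part (a): QTc formulas**

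Inputs: the two formulas in SAP 7.2.5 and the cut-offs in SAP Table 8. The QT and RR values are illustrative.

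The correct forms on this scale are QTcB = QT(msec) / RR(sec)^(1/2) and QTcF = QT(msec) / RR(sec)^(1/3). The printed forms replace RR(sec) by RR(sec) x 1000. The ratio of correct to printed therefore does not depend on QT or RR:

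- Bazett: 1000^(1/2) = 31.62
- Fridericia: 1000^(1/3) = 10.00

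| QT, RR | QTcB correct | QTcB printed | QTcF correct | QTcF printed |
|---|---|---|---|---|
| 400 msec, 1.0 sec | 400 | 400/√1000 = 12.6 | 400 | 400/10 = 40.0 |
| 440 msec, 0.8 sec | 440/√0.8 = 491.9 | 440/√800 = 15.6 | 440/0.8^(1/3) = 474.0 | 440/800^(1/3) = 47.4 |

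In the second row both correct values exceed 450 msec and neither printed value does. At RR 1 sec, a printed result above 450 would need QT above 450 x 31.62 = 14,230 msec (Bazett) or 450 x 10 = 4,500 msec (Fridericia). A printed increase above 30 would need a true increase above 30 x 31.62 = 949 msec or 30 x 10 = 300 msec.

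**Part (b): Table 6 note**

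Table 6 lists 4 hematology and 15 chemistry parameters, 19 in all, and every entry is an abnormal value. The parallel weight rule in SAP 9.12.3 (Table 7) counts subjects who met its criteria ("The frequencies and percentages of subjects who met MAPVS criteria at least once in the DSP-5423P post-baseline") and carries no such note. The intended reading is therefore that a value counts when it lies within the listed range.

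Subjects are counted on at least one qualifying value. Taken literally, the note counts every tested subject except those whose post-baseline values are all markedly abnormal.

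To show the size, SAP 8.5 gives 8 scheduled post-baseline laboratory visits ("W2, 6, 12, 20, 28, 36, 44, 52"). The documents give no abnormality rates, so assume a chance p that any one value is markedly abnormal, independent across k values:

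- intended rule counts 1 − (1 − p)^k of subjects
- literal note counts 1 − p^k of subjects

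| p | k = 8: intended | k = 8: literal | k = 1: intended | k = 1: literal |
|---|---|---|---|---|
| 1% | 7.7% | >99.9% | 1% | 99% |
| 5% | 33.7% | >99.9% | 5% | 95% |
| 20% | 83.2% | >99.9% | 20% | 80% |

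The k = 1 columns are the other extreme: a subject who stops early, or a fasting-only parameter for which the only fasting sample is the one at Visit 113 (the only post-baseline visit in the patch phase where Protocol 11.3.5 makes fasting mandatory).

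Independence is unrealistic for repeated values in one person, so consider persistence as well. Assume that of 100 subjects 2 are abnormal at every visit and 8 at some visits. The intended rule counts 2 + 8 = 10 and the literal note counts 100 − 2 = 98. The literal table is thus not the complement of the intended one, which would be 90, and the correct figures could not be recovered by subtraction.

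**The case against.** The strongest reply is that neither text is likely to reach a result.

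On QTc, the central reader calculates and reports the values. SAP 8.2 does not list QTc among its derived variables, although that list is not exhaustive. SAP section 3 declares no change from the protocol's analyses, and the protocol prints no formula. On this reading the formulas are descriptive and Table 8 is unaffected. That stands. It does not settle the matter fully, because 9.12.4 does not expressly say that the reported values are used as they are. SAP 8.7 prefers SAP-calculated values over values derived in EDC; that sentence sits among rating-scale rules and probably does not reach reader data, but it is a reason to name the source.

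The factor 1000 could in principle be a conversion artefact in the text version of the SAP. It appears identically in both formulas, which makes this unlikely, and the doubt does not touch the Table 6 note.

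On Table 6, the title, the column heading and the counting sentence make the intent plain. That also stands: this is a one-word slip. But nothing elsewhere in the SAP overrides the note, and a programmer who followed it would produce a wrong table. The percentages above rest on assumed rates and show only that the literal note counts almost everyone.

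Other safeguards remain. Investigators review out-of-range laboratory values and central ECG over-reads (Protocol 12.2). The Normal/Abnormal ECG table and the laboratory summaries and listings do not depend on either text.

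**Conclusion.** Both points hold, and both are minor.

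The QTc formulas are too small by exactly 31.62 (Bazett) and 10.00 (Fridericia). This follows from the printed text alone. The effect on the by-visit summaries and Table 8 is zero if the central reader's values are analysed, which is the natural reading. It is total for Table 8 if the printed formulas are programmed.

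The Table 6 note reverses the rule for a single value and, at subject level, would give percentages close to 100% for most parameters. The exact figures depend on the assumed rates and the assumed dependence between visits; the direction does not.

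Mean QTc values near 13 or 40 msec, or markedly abnormal rates near 100%, would be noticed before reporting. The case for correction is that a safety specification should be right as written, not that any result has been shown to be wrong.

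**What to change.** - **SAP 7.2.5:** replace the formulas with QTcB = QT(msec) / [RR(sec)]^(1/2) and QTcF = QT(msec) / [RR(sec)]^(1/3), or delete them.
- **SAP 9.12.4:** add a sentence stating that the QTcB and QTcF values reported by the central ECG reader feed the by-visit summaries and Table 8.
- **SAP 9.12.2, Table 6 note:** change *outside* to *within*.

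The cost is three one-line wording corrections, with no change to data collection, design or sample size.
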